### **10.3 Paediatric logistic organ dysfunction score (PELOD score) at 30 days post-randomisation**

The maximum and aggregate paediatric logistic organ dysfunction score (PELOD score) at 30 days following randomisation will be summarised, within each treatment group. Patients that die within 30 days post randomisation will be considered to have the maximum possible PELOD score (71 points) from the day of death onwards. Differences between the treatment groups will be compared using linear regression - adjusted for the same *a priori* baseline variables reported above. The results of the linear regression model will be reported adjusted, and unadjusted for comparison, with 95% confidence interval for the coefficients.

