#### 11.2 Time points for data collection

Baseline/randomisation;

- Daily during episode of acute respiratory failure;
- At discharge from the PICU (where relevant) and hospital;
- 30 days post-randomisation;
- 90 days post-randomisation;
- One year post-randomisation.

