#### 11.3 Data collected at baseline/randomisation

The following identifiers are required for flagging participants with the hospital patient management system/DLS and for follow-up at 30 days, 90 days and at one year post-randomisation:

- NHS number;
- date of birth;
- sex;
- forename;
- surname;
- full name, full address and telephone number of GP.

The following data are required for risk adjustment and stratification:

- chronic diagnosis;
- bone marrow transplantation (yes/no);
- suspected cause of acute respiratory failure;
- weight;
- PIM2 score.

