## 11.4 Data collected daily during this episode of acute respiratory failure

- physiology data, including FiO2, O2 l/min, PCO2, ScvO2, SpO2, blood lactate, heart rate, respiratory rate, work of breathing (normal/increased/greatly increased), serum creatinine, platelet count, white blood count;
- Glasgow Coma Score;
- PELOD score:
- type of ventilation;
- interventions, including use of sedative drugs.

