## 19.2 Statistical analysis

All analyses will be conducted by intention to treat, with a two-sided p value of <0.05 taken to indicate a statistically significant result. The primary effect estimate will be the relative risk of intubation for invasive mechanical ventilation at 30 days post-randomisation, with statistical significance assessed by Fisher's exact test. As a secondary analysis, the primary outcome will also be analysed by multivariable logistic regression adjusted for baseline covariates of age, chronic diagnosis, bone marrow transplantation, suspected cause of acute respiratory failure, weight and PIM2 score . The baseline covariates have been selected *a priori* for their anticipated strong association with the outcome, no further selection of covariates will be performed based on imbalance at baseline or significance in univariable analyses. Secondary outcomes will be analysed by logistic regression for binary outcomes (mortality, requirement of level 2/3 respiratory support) or linear regression for continuous outcomes (PELOD , days free from ventilator support/supplemental oxygen) adjusted for the same baseline covariates as above. Due to the small sample size, no subgroup analyses are planned.

A single interim analysis will be conducted at 50% recruitment. The results of the interim analysis will be reviewed by the DMEC, using a Peto-Haybittle stopping rule (P<0.001) to recommend early termination of the trial due to harm^20. It is not recommended that the trial should terminate early for efficacy, as any treatment effect that would be statistically significant at this level would be sufficiently large as to be clinically implausible and therefore unlikely to change clinical practice. Additional interim analyses will be conducted if requested by the DMEC.

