## 10. Secondary analyses

The subsequent secondary analyses will be adjusted using the following baseline covariates: age, weight, bone marrow transplantation and PIM2 score. The baseline covariates have been selected *a priori* for their anticipated strong association with the outcome. No further selection of covariates will be performed based on imbalance at baseline or significance in univariable analyses.

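### Maximum and aggregate PELOD are not adjusted for PELOD at randomisation, which costs some precision and leaves both estimates open to chance imbalance, without biasing them

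*SAP*

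**What the plan says.** SAP 10.3 analyses maximum and aggregate PELOD by linear regression, unadjusted and "adjusted for the same *a priori* baseline variables reported above". SAP 10 lists those variables as "age, weight, bone marrow transplantation and PIM2 score", and Tables 5b and 5c carry the same terms. The longer list in Protocol 19.2, "age, chronic diagnosis, bone marrow transplantation, suspected cause of acute respiratory failure, weight and PIM2 score", has no entry PELOD either. Nor do the baseline characteristics in SAP 8.2 and Table 1.

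Protocol 11.2 gives two separate collection points, one at baseline/randomisation and one labelled "Daily during episode of acute respiratory failure". PELOD appears only in Protocol 11.4, headed "Data collected daily during this episode of acute respiratory failure". Protocol 11.3, under "The following data are required for risk adjustment and stratification", includes PIM2 but not PELOD.

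Under SAP 10.3, a child who dies within 30 days scores 71 points from the day of death. Neither document says which day is the first to count towards the maximum or the aggregate.

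**The concern.** SAP 10 says that covariates were chosen because a strong association with the outcome was expected, but one list serves every secondary outcome. For an organ-dysfunction score, the same score at entry is the natural predictor. Respiratory failure must already be present for a child to be eligible (Protocol 6.1), and up to 24 hours may pass before treatment starts (Protocol 9.0). Children therefore arrive with differing amounts of organ dysfunction.

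Minimisation balances only age group and transplantation. If one arm happens to start sicker, the PELOD difference carries part of that gap, except for what PIM2 absorbs. Table 1 would not show the gap in PELOD terms. At stake are the width of two secondary confidence intervals and how readers interpret them. The primary Fisher comparison is unaffected.

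**Working it through.** **1. The plan's own figure, used only to bound the sample.** For 35% v 14%, 80% power and two-sided 5%:
- n = [1.960·√(2·0.245·0.755) + 0.842·√(0.35·0.65 + 0.14·0.86)]² / 0.21² = 64.65 per arm.
- With continuity correction, (n/4)·[1 + √(1 + 4/(0.21n))]² = 73.9, so 74 per arm and 148 in total. The stated figure is reproduced.

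It concerns intubation and says nothing about PELOD. SAP 12 reports that the 50% point was not reached, so fewer than 148/2 = 74 children in all. The checks use N = 72 (36 per arm) as the upper case and an assumed N = 30 as a small case.

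**2. Bias.** Allocation is independent of entry PELOD. In 8,000 simulated trials per setting (N from 30 to 148; assumed correlation ρ between entry score and outcome of 0.3, 0.5 or 0.7), the mean error was within 0.005 outcome SD with and without the covariate.

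**3. Chance imbalance** (simple 1:1 allocation, before any PIM2 adjustment). The SD of the between-arm difference in mean entry score is √(2/n per arm) baseline SDs.
- N = 72: √(2/36) = 0.236. A gap above 0.3 SD occurs in about 20% of trials. A one-SD gap moves the estimate by ρ × 0.236 = 0.07, 0.12 and 0.165 outcome SD for the three values of ρ.
- N = 30: √(2/15) = 0.365. A gap above 0.3 SD occurs in about 41% of trials, and the shifts are 0.11, 0.18 and 0.26 SD.

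**4. Precision, ignoring deaths.** The variance of the treatment coefficient falls to about 1 − ρ² = 0.91, 0.75 and 0.51. Simulated ratios were 0.93, 0.77 and 0.51 at N = 72, and 0.94, 0.77 and 0.53 at N = 30. At N = 30 about 3–4% of the variance is lost to estimating the extra coefficient (for example 0.943/0.91 = 1.036).

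With PIM2 already in the model, the ratio is 1 − r², where r = (r_yb − r_yp·r_bp)/√[(1 − r_yp²)(1 − r_bp²)]. Here y is the outcome, b is entry PELOD and p is PIM2. All three correlations are assumed:

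| r_yb | r_yp | r_bp | r | variance ratio |
|---|---|---|---|---|
| 0.3 | 0.3 | 0.5 | 0.18 | 0.97 |
| 0.5 | 0.4 | 0.5 | 0.38 | 0.86 |
| 0.7 | 0.5 | 0.6 | 0.58 | 0.67 |

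**5. Precision with deaths scored 71.** Simulation of 300,000 children per setting, with these assumptions:
- entry score gamma, shape 1.6 and scale 6 (mean 9.6, SD 6·√1.6 = 7.6);
- a survivor's maximum is the entry score plus a non-negative worsening (SD 10 before truncation);
- log-odds of death rise by 0–0.7 per SD of entry score;
- a PIM2-like covariate, correlated 0.3–0.6 with entry score, is already in the model.

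| Mortality | Cut in residual variance, maximum PELOD |
|---|---|
| 0% | 52–61% |
| 10% | 5–26% |
| 20% | 1–20% |
| 50% | 1–12% |

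For aggregate PELOD the cut is about 0–12% once deaths occur. In interval width, a 26% cut gives √0.74 = 0.86 (14% narrower), a 12% cut gives √0.88 = 0.94 (6% narrower), and a 1% cut gives almost nothing.

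**6. The first day counted.** Take one entry value and one later value, correlated 0.3–0.7. If the entry value is allowed into the maximum, a true shift of −0.50 SD in the later value shows as only −0.19 to −0.21 SD. Covariate adjustment does not undo this dilution. Only a defined window does.

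**The case against.** The case for leaving the models alone is substantial.

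- **Randomisation already deals with bias.** This stands. A reader might infer that pre-existing organ dysfunction distorts the treatment effect, or that a high entry score acting as a floor under the maximum favours one arm. Neither follows. Entry dysfunction is balanced in expectation, the floor applies to both arms alike, and a valid interval already allows for chance imbalance. Only a narrower interval and an estimate less sensitive to the particular imbalance remain to be gained.
- **Severity is partly covered by PIM2, in a fixed list.** This stands in part. PIM2 shrinks the gain without removing it (step 4). SAP 10 rules out choosing covariates on observed imbalance or univariable significance, and a term prespecified on principle is neither.
- **A pre-randomisation PELOD is not documented.** This stands. A reader might infer from daily scoring within an episode that precedes randomisation that an entry score must be in the data. The documents do not say when daily scoring starts, and Protocol 11.3 leaves PELOD out. SAP 8 mentions no such score. The SAP is dated September 2016 and recruitment was planned to end in January 2016, so a new baseline item could not be collected prospectively. Multiple imputation cannot supply a variable that was never recorded.
- **Deaths dominate the scores.** This stands and limits the size. Protocol 2.0 cites case fatality of around 20% in children with acute lung injury or ARDS, approaching 50% with immunocompromise. Ward patients in this trial may fare better.

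**Conclusion.** The omission is real and minor. Both PELOD models leave out the entry value of their own outcome. The consequence is lost precision and exposure to chance imbalance in two secondary outcomes, and a claim of bias is not supported. At 10–50% mortality the likely gain is modest for maximum PELOD and small for aggregate PELOD. At the low end it would be offset by the cost of estimating one more coefficient in a small trial. The large gain of 52–61% needs no deaths at all and should not be expected.

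These sizes rest on an assumed entry distribution, assumed correlations and an assumed link between entry score and death. The documents give none of these, nor the achieved sample size. A narrower spread of entry scores is plausible, given the exclusions in Protocol 6.2, and would reduce the gain. The undefined first scoring day does not depend on these assumptions and needs settling whether or not the covariate is added.

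**What to change.** 1. In SAP 10.3, state the first post-randomisation day that counts towards maximum and aggregate PELOD.
2. Establish, before outcomes are compared by arm, whether PELOD can be scored from values recorded before randomisation.
3. If it can, report it by arm in SAP 8.2 and Table 1, and add it as a prespecified covariate to the linear models of Tables 5b and 5c. Handle scattered missing values with the multiple imputation already planned in SAP 7.
4. If it cannot, say so and keep the current model. Do not substitute a day-of-randomisation score that includes time on treatment, because that would adjust for a post-treatment value.
5. Leave the logistic models unchanged. SAP 9 has already shortened their covariate list because of the smaller sample.

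The cost is one degree of freedom in two models, one Table 1 row and a check of what was recorded before randomisation.

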### **10.4 Days free from any ventilator support at 30 days post-randomisation**

The mean number of days free from any ventilator support up to 30 days following randomisation, within each treatment group will be reported. Patients that die within 30 days post-randomisation will be considered to have zero days free from any ventilator support. Differences between the treatment groups will be compared using linear regression - adjusted for the same *a priori* baseline variables reported above. The results of the linear regression model will be reported adjusted, and unadjusted for comparison, with 95% confidence interval for the coefficients.

### **10.5 Days free from supplemental oxygen at 30 days post-randomisation**

The mean number of days free from any supplemental oxygen ventilator support up to 30 days following randomisation, within each treatment group will be reported. Patients that die within 30 days post-randomisation will be considered to have zero days free from supplemental oxygen. Differences between the treatment groups will be compared using multilevel linear regression - adjusted for the same *a priori* baseline variables reported above. The results of the multilevel linear regression model will be reported adjusted, and unadjusted for comparison, with 95% confidence interval for the coefficients.

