#### and

3) either acute respiratory failure or acute on chronic respiratory failure as defined below.

Acute respiratory failure is defined as a new onset of hypoxaemia, tachypnoea and chest x-ray changes developing in the previous 48 hours. All of the following age specific criteria must be met:

i.hypoxaemia: arterial oxygen saturation (SpO2) less than 90% in room air

and

ii.tachypnoea: respiratory rate greater than approximate 90th centile for age: 55 (<12 months); 45 (12 months – <2 years); 30 (≥2 years – <4 years); 25 (≥4 years – <10 years) and 20 (≥10 years – <18 years)

[unless the child is receiving a continuous infusion of an opiate at any dose, in which case the tachypnoea criteria do not apply]

and

iii. *chest X-ray changes*: radiological evidence of acute pulmonary infiltrates developing in the previous 48 hours.

Acute on chronic respiratory failure is defined as a significant acute deterioration, in the previous 48 hours, in infants and children with pre-existing chronic lung disease

requiring long-term supplemental oxygen therapy. All of the following age-specific criteria must be met:

i. *hypoxaemia*:  $SpO_2$  less than 90% in room air and a requirement for increased supplemental oxygen by  $\geq$ 30% of baseline flow rate (or  $\geq$ 30% increase from baseline fraction of inspired oxygen (FiO2)where measured).

and

ii. tachypnoea: increased respiratory rate >20% above baseline and greater than approximate  $90^{th}$  centile for age: 55 (<12 months); 45 (12 months – <2 years); 30 ( $\geq$ 2 years – <4 years); 25 ( $\geq$ 4 years – <10 years) and 20 ( $\geq$ 10 years – <18 years)

[unless the child is receiving a continuous infusion of an opiate at any dose, in which case the tachypnoea criteria do not apply]

and

iii. *new chest X-ray changes:* radiological evidence of acute pulmonary infiltrates developing in the previous 48 hours.

[The cause of acute or acute on chronic respiratory failure is not a consideration. This is a pragmatic trial to assess the response of the clinical syndrome of acute respiratory failure to two different management strategies. Acute respiratory failure might arise from an acute lower respiratory tract infection, systemic sepsis or inflammatory processes, such as veno-occlusive disease, or graft vs. host disease with varying degrees of fluid retention/overload.]

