### **3.3.2 Secondary**

The secondary outcome measures are:

- maximum and aggregate paediatric logistic organ dysfunction score (PELOD) at 30 days post-randomisation;
- mortality at 30 days post-randomisation;
- requirement for Level 2 or Level 3 respiratory support within 30 days post-randomisation;
- days free from any ventilator support (Level 2, 3 or 4 respiratory support) at 30 days post-randomisation;

- days free from supplemental oxygen (i.e. above pre-acute respiratory failure requirement) at 30 days post-randomisation;
- hospital mortality;
- mortality at 90 days post-randomisation; and
- mortality at one year post-randomisation.

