## Appendix 1: Dummy tables and figures

### Proposed tables

i. Table 1: Comparison of baseline characteristics by treatment group

	Variables	Early CPAP	Usual treatment
		N=XX	N=XX
Age group	0-11 months, n (%)	XX (XX.X)	XX (XX.X)
	12 months or older, n (%)	XX (XX.X)	XX (XX.X)
	[N]	[XX]	[XX]
Age (months)	mean (SD)	XX.X (XX.X)	XX.X (XX.X)
	median (IQR)	XX (XX, XX)	XX (XX, XX)
	[N]	[XX]	[XX]
Gender	Male, n (%)	XX (XX.X)	XX (XX.X)
	Female, n (%)	XX (XX.X)	XX (XX.X)
	[N]	[XX]	[XX]
Weight (kg)	mean (SD)	XX.X (XX.X)	XX.X (XX.X)
	median (IQR)	XX.X (XX.X, XX.X)	XX.X (XX.X, XX.X)
	[N]	[XX]	[XX]
Acute respiratory failure criteria met	Acute respiratory failure, n (%)	XX (XX.X)	XX (XX.X)
	Acute on chronic respiratory failure, n (%)	XX (XX.X)	XX (XX.X)
	[N]	[XX]	[XX]
Bone marrow transplant	Yes, n (%)	XX (XX.X)	XX (XX.X)
	No, n (%)	XX (XX.X)	XX (XX.X)
	[N]	[XX]	[XX]
Cause of impaired immunity*	High risk of severe neutropenia, n (%)	XX (XX.X)	XX (XX.X)
	Severe immunodeficiency, n (%)	XX (XX.X)	XX (XX.X)
	Haemophagocytic lymphohistiocytosis, n (%)	XX (XX.X)	XX (XX.X)
	Undergoing bone marrow transplantation, n (%)	XX (XX.X)	XX (XX.X)
	Other condition/therapy, n (%)	XX (XX.X)	XX (XX.X)
[N]	[XX]	[XX]	
Suspected main cause of acute respiratory failure	Viral pneumonitis, n (%)	XX (XX.X)	XX (XX.X)
	Bacterial chest infection, n (%)	XX (XX.X)	XX (XX.X)
	Graft-versus-host disease, n (%)	XX (XX.X)	XX (XX.X)
	Fluid overload, n (%)	XX (XX.X)	XX (XX.X)
	Veno-occlusive disease, n (%)	XX (XX.X)	XX (XX.X)
	Other condition/therapy*, n (%)	XX (XX.X)	XX (XX.X)
[N]	[XX]	[XX]	
PIM2r score	mean (SD)	XX.X (XX.X)	XX.X (XX.X)
	median (IQR)	XX (XX, XX)	XX (XX, XX)
	[N]	[XX]	[XX]
Supplemental O2 requirement (pre-acute respiratory failure)	No, n (%)	XX (XX.X)	XX (XX.X)
	Yes, n (%)	XX (XX.X)	XX (XX.X)
	[N]	[XX]	[XX]

\* patients may have more than one cause of impaired immunity; n: number of patients; %: percentage of patients; N: total number of patients; SD: standard deviation; IQR: interquartile range

ii. Table 2: Comparison of clinical management by treatment group

Variables		Early CPAP	Usual treatment
		N=XX	N=XX
PICU admission	No, n (%)	XX (XX.X)	XX (XX.X)
	Yes, n (%)	XX (XX.X)	XX (XX.X)
	[N]	[XX]	[XX]
Length of stay in PICU (days)	mean (SD)	XX.X (XX.X)	XX.X (XX.X)
	median (IQR)	XX.X (XX.X, XX.X)	XX.X (XX.X, XX.X)
	[N]	[XX]	[XX]

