ix. Table 5e: Logistic regression model for requirement for Level 2 or Level 3 respiratory support within 30 days post-randomisation

Variables	Odds ratio	95% CI	P-value
Treatment			
Usual treatment	1		
Early CPAP	X.XX	X.XX, X.XX	0.XXX
Age (per year)	X.XX	X.XX, X.XX	0.XXX
Weight (per 5kg)	X.XX	X.XX, X.XX	0.XXX
Bone marrow transplantation			
No	1		
Yes	X.XX	X.XX, X.XX	0.XXX
PIM2r score (per point)	X.XX	X.XX, X.XX	0.XXX

x. Table 5f: Linear regression model for days free from any ventilator support at 30 days post-randomisation

Variables	Coefficient	95% CI	P-value
Constant	X.XX	X.XX, X.XX	0.XXX
Treatment			
Usual treatment	0		
Early CPAP	X.XX	X.XX, X.XX	0.XXX
Age (per year)	X.XX	X.XX, X.XX	0.XXX
Weight (per 5kg)	X.XX	X.XX, X.XX	0.XXX
Bone marrow transplantation			
No	0		
Yes	X.XX	X.XX, X.XX	0.XXX
PIM2r score (per point)	X.XX	X.XX, X.XX	0.XXX

- xi. Table 5g: Linear regression model for days free from supplemental oxygen at 30 days post-randomisation

Variables	Coefficient	95% CI	P-value
Constant	X.XX	X.XX, X.XX	0.XXX
Treatment			
Usual treatment	0		
Early CPAP	X.XX	X.XX, X.XX	0.XXX
Age (per year)	X.XX	X.XX, X.XX	0.XXX
Weight (per 5kg)	X.XX	X.XX, X.XX	0.XXX
Bone marrow transplantation			
No	0		
Yes	X.XX	X.XX, X.XX	0.XXX
PIM2r score (per point)	X.XX	X.XX, X.XX	0.XXX

- xii. Table 5h: Logistic regression model for hospital mortality

Variables	Odds ratio	95% CI	P-value
Treatment			
Usual treatment	1		
Early CPAP	X.XX	X.XX, X.XX	0.XXX
Age (per year)	X.XX	X.XX, X.XX	0.XXX
Weight (per 5kg)	X.XX	X.XX, X.XX	0.XXX
Bone marrow transplantation			
No	1		
Yes	X.XX	X.XX, X.XX	0.XXX
PIM2r score (per point)	X.XX	X.XX, X.XX	0.XXX

- xiii. Table 5i: Logistic regression model for mortality at 90 days post-randomisation

Variables	Odds ratio	95% CI	P-value
Treatment			
Usual treatment	1		
Early CPAP	X.XX	X.XX, X.XX	0.XXX
Age (per year)	X.XX	X.XX, X.XX	0.XXX
Weight (per 5kg)	X.XX	X.XX, X.XX	0.XXX
Bone marrow transplantation			
No	1		
Yes	X.XX	X.XX, X.XX	0.XXX
PIM2r score (per point)	X.XX	X.XX, X.XX	0.XXX

[figure not shown]
xiv. Table 5j: Logistic regression model for mortality at one year post-randomisation

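### SAP 10.5 conflicts with the trial's own definition of oxygen-free days and names a multilevel model without a level

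*SAP*

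**What the plan says.** **Outcome.** SAP 3.3.2 lists "days free from supplemental oxygen (i.e. above pre-acute respiratory failure requirement) at 30 days post-randomisation", and Protocol 5.2 has the same definition. SAP 10.5, which instructs the analyst, reports "The mean number of days free from any supplemental oxygen ventilator support up to 30 days following randomisation". The reference to the pre-illness requirement is gone, the word *any* has been added, and the mention of ventilator support appears to come from SAP 10.4. The only zero-day rule in 10.5 is for deaths: "Patients that die within 30 days post-randomisation will be considered to have zero days free from supplemental oxygen".

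**Population.** Protocol 6.1 admits acute-on-chronic respiratory failure, defined in children with chronic lung disease "requiring long-term supplemental oxygen therapy".

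**Model.** SAP 10.5 states: "Differences between the treatment groups will be compared using multilevel linear regression". It repeats the term when describing how results will be reported, and names no level, cluster or random effect. Protocol 19.2 gives "linear regression for continuous outcomes" and lists days free from supplemental oxygen among them. The dummy table is titled "Table 5g: Linear regression model for days free from supplemental oxygen at 30 days post-randomisation".

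**The concern.** Section 10 and the dummy tables are what an analyst programs from, and neither restores the baseline qualifier. For a child who was never on oxygen before the illness, the two wordings give the same count. For a child on long-term oxygen they can give opposite ends of the scale: full credit for recovery under SAP 3.3.2, or the score of a death under the literal 10.5.

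The model wording leaves a second choice open on the same outcome, since someone must decide whether to fit a multilevel model and at what level. SAP section 1 says the document exists to avoid decisions driven by the data. The SAP is dated 22/09/2016, and SAP 4 puts the planned end of recruitment at January 2016, so on that schedule the 30-day data already existed. That is a reason to close both choices in writing before analysis.

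**Working it through.** **1. The plan's own figures.** Neither document gives a sample size, SD or target difference for this outcome. The one sample-size figure, 148 for the primary outcome, reproduces: the continuity-corrected two-proportion formula for 35% versus 14%, two-sided 5% and 80% power gives 74 per arm (65 without the correction). It does not bear on this point.

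**2. The definitions applied to one child.** Take a surviving child who uses long-term oxygen every day and spends *r* of the 30 days above the pre-illness requirement.
- SAP 3.3.2 and Protocol 5.2: score = 30 − *r*.
- SAP 10.5 read literally: score = 0, since no day is free of any oxygen.
- A child who dies within 30 days: score = 0 (SAP 10.5).

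**3. Effect on the treatment difference, arms balanced.** Let *q* be the share of such children in each arm, *d* the true difference among the others, and *d_c* the true difference among these children on the defined outcome.
- Defined outcome: (1 − *q*)·*d* + *q*·*d_c*.
- Literal 10.5: (1 − *q*)·*d*, because all these children score 0 in both arms.

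The loss is *q*·*d_c*. If *d_c* = *d*, the difference shrinks by the fraction *q*; if treatment does nothing for these children, the difference does not shrink.

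*Illustration, all inputs assumed:* mean 15 days, SD 10 and *d* = *d_c* = 5 days. The SD under the literal reading is √[(1 − *q*)(10² + 15²) − ((1 − *q*)·15)²], and power ≈ Φ(difference / (SD·√(2/n)) − 1.96). For *q* = 10%: difference 0.9 × 5 = 4.5; variance 0.9 × 325 − 13.5² = 110.25, so SD 10.5; with n = 74, 4.5/(10.5 × √(2/74)) − 1.96 = 0.65, so power is 74%.

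| *q* | Difference (days) | SD | Power, 74 per arm | Power, 20 per arm |
|---|---|---|---|---|
| 0% | 5.00 | 10.0 | 86% | 35% |
| 5% | 4.75 | 10.28 | 80% | 31% |
| 10% | 4.50 | 10.5 | 74% | 27% |
| 20% | 4.00 | 10.77 | 62% | 22% |
| 30% | 3.50 | 10.83 | 50% | 17% |

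With these inputs the 0% row is also the result under the defined outcome. The planned size was 74 per arm. SAP 12 says half of recruitment was not reached, so the real total is below 74. The 20 per arm is an assumption.

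**4. Effect of imbalance.** If the arms differ in *q* by Δ*q*, the literal reading shifts the difference by about Δ*q* × mean. A 10-point imbalance with an assumed mean of 15 days gives 0.10 × 15 = 1.5 days. Protocol 9.0 minimises on age group and bone marrow transplantation. SAP 10 adjusts for age, weight, bone marrow transplantation and PIM2. Neither includes baseline oxygen use.

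**5. The model.** The outcome is one count per child, so there are no repeated values within a child to form a level. Table 5g has rows only for a constant, treatment and the four covariates. No other analysis in SAP 10 is multilevel, and 10.4, for the companion outcome of ventilator-free days, uses linear regression.

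**The case against.** The strongest reply is that these are two drafting slips in one paragraph. Most of the detail behind that reply stands, and it limits what can be claimed.

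- A reader might infer that the SAP has redefined the outcome as freedom from any oxygen. The documents do not support that. The sentence is garbled, SAP 3.3.2 in the same document keeps the qualifier, and nothing announces a change.
- A reader might infer a rule that scores children on long-term oxygen as zero. There is none; the written zero is for deaths. The zero follows only from the literal reading, and only for a child on oxygen every day. Protocol 6.1 says long-term, not continuous, and no section says how a part-day of oxygen counts.
- A reader might infer that no second level exists and the model cannot be fitted. SAP 3.1 and 8.1 refer to participating sites, so site is conceivable. What can be said is that no level is named.
- Under randomisation, imbalance is noise and not systematic bias. The expected effect of the literal reading is dilution.
- SAP 10.4 concerns a different outcome, so it supports by analogy only.

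What remains is that 10.5, followed as written, departs from the defined outcome for a group the protocol explicitly enrols, and that its model disagrees with both the protocol and the SAP's own table.

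**Conclusion.** The point holds as an internal conflict that should be reconciled before this outcome is analysed. As written, 10.5 contradicts Protocol 5.2 and SAP 3.3.2 on what is counted, and Protocol 19.2 and Table 5g on the model.

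Under the literal reading the difference is diluted roughly in proportion to the share of children on daily long-term oxygen. An assumed share of 5% to 30% gives 5% to 30% dilution, provided the treatment effect in these children resembles that in the others. If few were enrolled, the effect is near nothing. Any figure in days is illustrative, because the documents give no share, mean, SD or final sample size. One secondary outcome is affected and the primary analysis is not.

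**What to change.** 1. In SAP 10.5, replace the garbled phrase with the SAP 3.3.2 definition, counting days free from supplemental oxygen above the pre-illness requirement. Delete *any* and *ventilator support*.
2. State how an oxygen-free day is counted for a child with a baseline requirement, including a part-day.
3. Confirm that the baseline requirement is available as a flow or FiO2. SAP 8.2 lists it, but Table 1 shows the item, supplemental oxygen "requirement (pre-acute respiratory failure", only as Yes/No, and Protocol 11.3 does not list it. Acute-on-chronic eligibility already compares against baseline flow or FiO2, and Protocol 11.4 collects oxygen flow and FiO2 daily during the episode, so the amount should be retrievable.
4. Replace multilevel linear regression, in both places, with linear regression to match Protocol 19.2 and Table 5g. If a level was intended, name and justify it.

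Items 1, 2 and 4 cost only a text change. Item 3 costs a check of the case report form, and retrieval from screening or medical records for the acute-on-chronic children if only Yes/No was captured.
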